Eligible participants who agree to proceed with the study will be invited to meet with a registered dietitian or trained research personnel who will instruct them on how to complete a dietary food record, explain the details regarding following a low-polyphenol diet throughout the intervention, and provide instruction of foods to avoid prior to the pharmacokinetic trial at wk 0. Prior to the initial pharmacokinetics trial, participants will be asked to collect 3 days of fecal samples and return to the study center to participate in a sugar probe test. After completing the sugar probe test, participants will return to the study center at least 3 days after to complete a 12-h pharmacokinetics trial. Afterwards, participants will be provided a 2-wk supply of GTE-rich or placebo confections. After 2 wk, fasting blood will be collected from the participants and the other 2-week supply of confections will be provided for the remainder of the study. Upon completing the 4-week intervention, participants will complete a second sugar probe test. We estimate that completion of all study procedures will take 6-8 wk per participant. Each step of the study procedure will be discussed in detail below. See *Study Design* attachment for an overview of the study.

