
In the event that a participant is telephoned and is unavailable, a message will be left requesting a callback at a convenient time or that a member of the study team will try calling again at a later

time. No confidential or sensitive information will be shared with third parties or left on answering machines.

Dietary Meeting. Eligible participants who meet the study inclusion criteria, a dietary meeting will be scheduled with a registered dietitian or trained individual (i.e. nutritional sciences graduate student) from the research team. During the dietary meeting, the dietitian/trained individual will show the participant how to properly complete the 3-d diet record (see *Diet Record Form* attachment). Participants are expected to follow a low-polyphenol diet throughout the intervention to avoid potential confounding effects on the study outcomes. The dietitian/trained individual will clearly identify polyphenol-rich foods/drinks participants should avoid during the study and inform them to record if they accidentally consume any polyphenol-rich foods/drinks during the study (see *List of Polyphenol-Rich Foods* and *Polyphenol Intake Record* attachments). The dietitian/trained individual will inform the participant of key foods to avoid, which includes any type of tea, coffee, fruits, fruit juices, chocolate, nuts, legumes, and wine. These foods are known to be rich in polyphenols, and consumption may confound the interpretation of the pharmacokinetics trial and intervention. In addition to dietary advice, the participant will be informed of the proper way to collect their urine and feces using the provided sterile collection containers. Fecal samples will be collected by the participant from 3 days prior to the pharmacokinetics trial. Participants will be provided a cooler with ice to store their fecal samples for up to 24 hours. The participant will then return their samples to the study center or coordinate with study personnel to meet at a public and mutual location and return their samples within 24 hours from collection.

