The participant will be instructed to abstain from exercise for 24 hours prior to their sugar probe test and pharmacokinetics trial. For each visit to our study center, participants will be instructed to be fasted for 10-12 hours to ensure reliable blood sampling. Participants will be instructed to complete the dietary record for 3-d before the pharmacokinetics trial and second sugar probe test (wk 0 and 4) and their wk 2 study center visit.

Test Trials. Participants will be block randomized into two groups to receive either a GTE-rich or placebo (without GTE) confection. Participants will complete a pharmacokinetics trial prior to starting the intervention. Prior to (wk 0) and following 4-wk intervention, participants will collect 3 days of fecal samples and complete a sugar probe test. For this study, each participant will visit the study center a total of 6 times, including the screening and dietary meetings, to complete individual test trials. For each study center visit, participants will report in a fasted state (10-12 hours).

Prior to the first study visit, participants will complete a 3-d diet record. At the first study visit, participants will perform a sugar probe test. This test will consist of participants ingesting a test beverage of 40 g sucrose, 5 g lactulose, 1 g mannitol, and 1 g sucralose dissolved in water (500 mL). After ingestion, the participants will be provided a standardized sucrose-free meal within the first 5 hours and water throughout. Urine will be collected from 0-5 and 6-24 hours in provided containers.

The second study visit will be scheduled at least 3 d after the sugar probe test. The second study visit will consist of a 12-h pharmacokinetics trial. Participants will ingest one-half the daily GTE-rich confections (0.5 g GTE). Blood will then be collected at the following hourly time points: 0 (before confection ingestion), 0.25, 0.5, 1, 2, 3, 5, 8, 10, 12 h. Urine will be collected between 0-4, 4-8, 8-12, and 12-24 h post-ingestion into provided urinary collection containers. During the pharmacokinetics trial, participants will be allowed free access to water and provided a standardized-polyphenol free meal.

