Pharmacokinetics Trial. Within 3-d after completing the first sugar probe test, participants will return to the study center to perform a 12-h pharmacokinetics trial. At least 3-d prior to the pharmacokinetics trial, participants will abstain from polyphenol-rich foods and drinks, including any type of tea, coffee, fruits, fruit juices, any chocolate (dark, milk), nuts, legumes (soy), and wine. Participants will arrive to the study center after abstaining from food and only consuming water for 10-12 hours. Participants will be provided a 15-min rest period, prior to the first blood collection. During the rest period, the participants will sit in a phlebotomy chair and a flexible catheter will be inserted into a forearm vein by a trained phlebotomist. After a 15-min sitting rest period, a blood sample will be obtained from a 3-way stopcock connected to the end of the catheter. Blood will be collected with a syringe and transferred to appropriate tubes for processing and subsequent determination of biochemical measurements. Following the first blood collection, participants will consume 3 GTE-rich confections (0.5 g GTE). Blood samples will be collected at 0 (prior to ingestion), 0.25, 0.5, 1, 2, 3, 5, 8, 10, and 12 h. Additionally, urine will be collected between 0-4, 4-8, 8-12, and 12-24 h. During the 12 h trial period, participants will be able to freely move and walk around if they choose to, as long as they stay in close proximity to the study center. We will provide a dedicated office space for participants to sit down in between blood draws. If the participant chooses to move around, we will wrap their arm with a bandage to minimize any risks and ensure the catheter stays in place to prevent the need to insert a needle again. Additionally, a person of the research team will escort and monitor the participant if they choose to move around the study center. After each blood sample is obtained, the catheter will be flushed with saline to prevent the formation of clots and to minimize the likelihood of having to insert a needle again. At 4 hours, each participant will be provided with a standardized polyphenol-free meal. A trained phlebotomist will perform all cannula insertions, needle sticks, and blood collections. After the 12 h trial, participants will be provided with a light snack (e.g. granola bar) and prepared standardized polyphenol-free meals to consume for the remainder of the 24-h urine collection period. Participants will also be provided with a 2-wk supply of GTE-rich or placebo confections. Participants will be advised to consume 6 confections each day (2 per meal; 1 g GTE/d) for the entire 4-week intervention study. Participants will be contacted periodically by email, text, or phone, by research personnel to provide polite reminders to enhance study compliance.

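### The week-0 schedule contradicts itself on the gap between sugar probe and pharmacokinetics trial, and leaves open whether baseline stools are collected before or after the probe drink

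*Combined protocol and SAP*

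**What the plan says.** All the relevant text is in section III.D of the combined protocol and SAP.

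- **Gap from sugar probe to PK trial.** Overview of Study Procedures: "After completing the sugar probe test, participants will return to the study center at least 3 days after to complete a 12-h pharmacokinetics trial". Test Trials: "The second study visit will be scheduled at least 3 d after the sugar probe test". Pharmacokinetics Trial: "Within 3-d after completing the first sugar probe test, participants will return to the study center to perform a 12-h pharmacokinetics trial".
- **Baseline stools.** In the Overview, participants "collect 3 days of fecal samples and return to the study center to participate in a sugar probe test", and that sentence begins by placing these steps ahead of the PK trial. The Dietary Meeting, where participants are told how to collect, says only: "Fecal samples will be collected by the participant from 3 days prior to the pharmacokinetics trial". Test Trials names stools and probe together for both week 0 and week 4 without stating an order. Microbiota Composition (III.C) says only that stools come from 3 days in each of those weeks.
- **Baseline diet record.** The end of the Dietary Meeting section says: "Participants will be instructed to complete the dietary record for 3-d before the pharmacokinetics trial and second sugar probe test". Test Trials says: "Prior to the first study visit, participants will complete a 3-d diet record". The first study visit is the sugar probe.

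The probe drink contains 40 g sucrose, 5 g lactulose, 1 g mannitol and 1 g sucralose. It is taken in the morning, and sucrose-free meals are supplied for the following 24 hours (Sugar Probe Test).

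**The concern.** Staff who work from the Pharmacokinetics Trial section could book PK for the day after the probe, which two other sections forbid. Staff who work from those sections could book it a week later, which the Pharmacokinetics Trial section forbids. Because the Dietary Meeting ties stool collection only to PK, and PK follows the probe, its wording permits (but does not require) baseline stools after the drink.

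This matters because change in gut microbiota is the third stated objective, and the same stools supply fecal calprotectin. The protocol keeps sugar alcohols out of the confections on the ground that they change the microbiota and would confound the results (GTE-rich Confections in III.A; Intervention Phase in III.D). Mannitol, in the probe drink, is a sugar alcohol. If some baseline stools follow the drink and others precede it, the baseline carries added variation. If week-4 stools stand in a different relation to the drink, a pre-post shift could arise that has nothing to do with the confection.

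**Working it through.** The plan gives no figure to reproduce, so the check enumerates the calendar.

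**Inputs.** Let *g* be the number of days from probe to PK.

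- Overview and Test Trials: *g* ≥ 3.
- Pharmacokinetics Trial: *g* ≤ 3.
- Together: *g* = 3 only.

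**Assumption for the stool count.** Read the Dietary Meeting sentence as the three calendar days immediately before PK: days PK−3, PK−2 and PK−1. The drink is taken on day PK−*g*. Then:

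- stool days on or after the drink day = min(*g*, 3);
- stool days strictly after the drink day = min(*g* − 1, 3).

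| Gap *g* (days) | Meets Overview and Test Trials | Meets Pharmacokinetics Trial | Stool days before / on / after drink day | On or after | Strictly after |
|---|---|---|---|---|---|
| 1 | no | yes | 2 / 1 / 0 | 1 | 0 |
| 2 | no | yes | 1 / 1 / 1 | 2 | 1 |
| 3 | yes | yes | 0 / 1 / 2 | 3 | 2 |
| 4 or more | yes | no | 0 / 0 / 3 | 3 | 3 |

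Because the drink is taken in the morning, a stool passed on the drink day could fall on either side of it.

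Under this reading no gap of 1 day or more puts all three stool days before the drink day, which is the order in the Overview. At *g* = 3, the one gap that all the interval statements allow, no stool day precedes the drink day. If the Overview's order is followed instead, the number of stools after the drink is 0 at every gap.

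**Diet record.** If the window is the three days immediately before PK, it contains the probe day (PK−*g*) only when *g* ≤ 3. At *g* = 3 the first record day is the probe day, when supplied meals replace habitual intake. A record completed before the first visit excludes the probe day at every gap.

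**The case against.** The strongest reply is that only the PK interval is a flat contradiction, while the claimed harm comes from the stool timing, which is merely ambiguous. The Overview sentence itself shows that the authors could describe stools as preceding PK and still mean before the probe: "Prior to the initial pharmacokinetics trial, participants will be asked to collect 3 days of fecal samples and return to the study center" for that test. The Dietary Meeting sentence can be read the same way. The counts above also rest on one optional reading, and the 3-day case takes its interval partly from the Overview while setting aside the Overview's stool order. This stands: the stool wording is ambiguous, and the counts are conditional.

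The mechanism is also an extrapolation. The protocol's reason for avoiding sugar alcohols concerns an ingredient eaten daily for 4 weeks, and by its title the supporting reference is a xylitol study in male mice. Nothing in the documents shows that a single 1 g dose of mannitol matters. This also stands.

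Both arms follow the same schedule, so the comparison of GTE with placebo is largely protected. That protection does not extend fully to the obese-versus-healthy comparison of microbiota, or to relating microbiota change to change in endotoxemia, since neither is a purely randomised contrast.

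The diet-record point is the weakest. A record kept before the first visit is also before PK, so the two statements clash only if the window is taken as the days immediately before PK.

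Finally, the Study Design attachment mentioned in the Overview is not among the documents and may show the intended order. It could not make a minimum and a maximum of 3 days agree in the text.

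**Conclusion.** The concern holds. The probe-to-PK interval is contradictory in current operational text, with *g* = 3 the only value that meets every statement. The stool instruction given at the dietary meeting permits between 0 and 3 of the 3 baseline stool days strictly after the drink day, depending on the gap, if it means the three calendar days before PK. The Overview's order gives 0. The diet record has two anchors that can diverge.

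The consequence is modest: possible noise and a possible pre-post shift in non-primary microbiota measures, of a size the documents do not allow one to estimate. The primary outcome is not affected by stool timing. Confidence is high that the texts need reconciling. That the drink would change the stool results is an inference. This should be corrected because the correction is nearly free, not because it endangers the main analysis.

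**What to change.** - Reconcile the Overview, Test Trials and Pharmacokinetics Trial sections to a single probe-to-PK interval. The choice of interval is the sponsor's.
- State in the Dietary Meeting, Test Trials and participant instructions that all three stools are collected before the sugar drink at both week 0 and week 4. The Overview already gives this order for week 0.
- Give the baseline diet record one window that excludes the probe day.
- Record the interval from each stool sample to the drink, so that any departure can be seen and examined in the microbiota analysis.

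The cost is wording in the protocol and participant instructions, plus one recorded date per stool sample. Return within 24 hours of collection already lets dates be largely inferred, so this last step is a small refinement. No visit or sample is added.

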Diet Assessment. Participants will be instructed to maintain a low-polyphenol diet throughout the study. Participants will record any consumption of polyphenol-rich foods throughout the study (a record sheet will be provided, see *Polyphenol Intake Record* attachment). Participants will be instructed to abstain from polyphenol-rich foods including tea of any kind, coffee, fruits, fruit juices, chocolate, nuts, legumes, and wine (a list will be provided, see *List of Polyphenol-Rich Foods* attachment). Food records (3-d) will be evaluated at wk 0, 2, and 4 using NDSR software and the NCC Flavonoid and Proanthocyanin database to assess energy, nutrient, and flavonoid intakes as we described (19, 71).

Plasma and Urine Catechin and Catechin-metabolites. To assess the absorption, metabolism, and excretion of green tea catechins during the pharmacokinetics trial (wk 0), plasma and urine catechin and catechin-metabolites will be measured by liquid chromatography-mass spectrometry (LC-MS). Green tea catechins (EGCG, ECG, EGC, EC) and their metabolites (e.g. valerolactones) will be measured using an adapted LC-MS method (72).

Metabolic Endotoxemia. Serum endotoxin will be measured at wk 0, 2, and 4 using a commercially available fluorometric assay that assesses endotoxin-mediated activation of recombinant Factor C and subsequent cleavage of a flurogenic substrate (PyroGene rFC; Lonza) as we detailed (43).

Gastrointestinal (GI) Permeability. A 4-sugar probe procedure appropriate for human clinical study will be performed as described (73). In brief, at wk 0 and 4, participants in the fasted state will ingest a 500-mL solution of sucrose (40 g), lactulose (5 g), mannitol (1 g) and sucralose (1 g) dissolved in water. Urine will be collected over a 24-hour period to assess GI permeability. Standardized sucrose-free meals (i.e. plain bagel, cream cheese, scrambled eggs, potato chips) will

be provided during the urine collection duration. Urinary sugars will be measured by LC-MS and permeability calculated as urinary excretion (%) and excretion ratios for sugars from 0-5 hours and 6-24 hours to reflect upper and lower GI permeability, respectively (74-77).

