Upon completing the pharmacokinetics trial, the intervention phase will begin. Participants will be provided a 2-week supply of GTE-rich or placebo confections. They will be advised to consume 6 confections/ every day (2 confections/meal; 1 g GTE/d) for the following 4-wk. After 2 wk of the intervention phase, participants will complete a 3-day diet record and return for their third study visit. At this visit, fasting blood will be collected. Participants will then receive their final 2-wk supply of confections. After 4 wk, participants will complete a final 3-d diet record and perform the sugar probe test once again as described above. During each study visit, participants will have access to drinking water and use of the restroom as needed.

Sugar Probe Test. On the morning of testing at wk 0 and 4, participants will arrive at the study center after abstaining from food and only consuming water for 10-12 hours. A sugar probe test will be conducted as described (73). Upon arrival, participants will be asked to empty their urinary bladder. Subsequently, they will then be asked to ingest a drink containing 40 g sucrose, 5 g lactulose, 1 g mannitol, and 1 g sucralose dissolved in water (500 mL). Within 2-hours after ingesting the sugar test beverage, participants will be asked to consume an additional 500 mL of water. Additionally, participants will be provided with standardized sucrose-free meals during the 24-h period. All foods consumed during the 24-hour period will be free of artificial sweeteners. Urine will be collected from 0-5 and 6-24 hours in sterile containers. For each urinary collection period, participants will be provided 2-L urine collection bottles and a Styrofoam cooler with ice packs to store collected urine until they return their samples the next day.

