
Intervention Phase / Test Confections. After completing the pharmacokinetics trial, participants will partake in a 4 wk intervention. Participants will be block randomized to receive a GTE-rich or placebo (no GTE containing) confection. Confections will be low carbohydrate and low calorie. Each serving (6 g) provides <15 kcal, while delivering 1 g of decaffeinated GTE. The catechin profile (82% catechins (w/w); 63% EGCG, 18% EGC, 10% ECG, 9% EC) is similar to that of freshly brewed green teas. Sucrose will be the main carbohydrate source because sugar alcohols alter microbiota composition (66) and would confound interpretation. Decaffeinated GTE was chosen to minimize potential side effects to prevent excess caffeine consumption or caffeine/drug interactions that could result during comorbidity management of metabolic conditions. Placebo confections will be identical to GTE-rich confections, but without GTE. Confections will be packaged in single-serve, oxygen impermeable containers, and coded for study blinding. Participants will be asked to store the confections in the refrigerator to maintain quality and freshness.

Participants will be asked to consume 6 confections each day (2 with each meal) for 4 weeks. Consumption of 6 GTE-rich confections is equivalent to delivering 1 g GTE/d. Participants will receive a 2-wk supply of confections after completing the pharmacokinetics trial. Halfway through the intervention (wk 2), participants will visit the study center in a fasted state (10-12 h). Participants will return any leftover confections. After a 5 min stabilization period, a single fasting blood sample will be collected following procedures stated above. After collecting blood, the participants will be provided the final 2-wk supply of confections. At the conclusion of the intervention phase (wk 4), participants will perform a second sugar probe test. Compliance will be evaluated based on the number of confections returned throughout the study.

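### The 24-hour exercise instruction does not cover the wk-2 fasting draw, one of the two on-treatment readings of serum endotoxin

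*Combined protocol and SAP*

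**What the plan says.** All references are to the combined protocol and SAP.

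- **Exercise.** The rule appears once, under Dietary Meeting in section III.D: "The participant will be instructed to abstain from exercise for 24 hours prior to their sugar probe test and pharmacokinetics trial".
- **Where those procedures fall.** For the sugar probe (section III.D, Sugar Probe Test): "On the morning of testing at wk 0 and 4, participants will arrive at the study center after abstaining from food". For the pharmacokinetics trial (section III.D, Test Trials): "Participants will complete a pharmacokinetics trial prior to starting the intervention". The wk-2 visit includes neither.
- **Fasting, in the same paragraph as the exercise rule.** "For each visit to our study center, participants will be instructed to be fasted for 10-12 hours to ensure reliable blood sampling". That paragraph also names the wk-2 visit explicitly for diet records.
- **Outcome.** Section III.C, Metabolic Endotoxemia: "Serum endotoxin will be measured at wk 0, 2, and 4 using a commercially available fluorometric assay". Section III.B, Power Calculation and Data Analysis, makes serum endotoxin the primary outcome, plans repeated measures ANCOVA for most data, and names no primary time point.
- **Rest before the draw.** At the pharmacokinetics visit: "Participants will be provided a 15-min rest period, prior to the first blood collection". At wk 2 (section III.D, Intervention Phase / Test Confections): "After a 5 min stabilization period, a single fasting blood sample will be collected following procedures stated above". No rest period is stated for wk 4.

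**The concern.** In a repeated measures analysis, preparation before each draw should be the same unless there is a reason for it to differ. Here the plan restricts exercise before the wk-0 visits and, on the natural reading, before the wk-4 visit. It is silent for the one in between, and no reason is given.

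Three things are exposed:

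1. Precision of any on-treatment summary that uses wk 2.
2. Interpretation of the within-person course from wk 0 to wk 2 to wk 4, because the instructions change at the middle point.
3. The obese-healthy comparison at wk 2. Health status is not randomised, so different exercise habits in the two groups could contribute to a difference there.

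The blood chemistries taken at wk 0, 2 and 4 (glucose, insulin, circulating inflammation markers) are in the same position. Fecal calprotectin is not, since feces are collected only at wk 0 and 4.

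**Working it through.** **Step 1: coverage by visit.** The plan counts six visits including the screening and dietary meetings. That leaves 6 - 2 = 4: first sugar probe, pharmacokinetics trial, wk 2, second sugar probe.

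| Visit | Fast stated | Exercise rule | Seated rest before draw |
|---|---|---|---|
| Wk 0, sugar probe | yes | yes | not stated |
| Wk 0, pharmacokinetics | yes | yes | 15 min |
| Wk 2, fasting draw | yes | **no** | 5 min |
| Wk 4, sugar probe | yes | yes (inferred) | not stated |

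The wk-4 entry rests on two inferences. The first is that the singular reference to the sugar probe test means both tests. The second is that wk-4 blood is drawn at that visit, which follows from the visit count because the sugar probe section describes no draw.

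**Step 2: the plan's own power figures.** The plan states more than 90% power for GTE vs placebo in obese adults and 80% for the interaction, with 20 obese and 20 healthy adults. It gives no mean, SD or correlation, so these cannot be reproduced. As a consistency check, assume 10 per cell, two-sided alpha 0.05 and no effect in healthy adults:

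- Interaction at 80%: (1.960 + 0.842) x sqrt(4/10) = 1.77 SD.
- Obese contrast at that effect: 1.77 / sqrt(2/10) = 3.96; 3.96 - 1.96 = 2.00; power about 97.7%, in line with the stated figure.
- Exactly 90% for the obese contrast: (1.960 + 1.282) x sqrt(2/10) = 1.45 SD.

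**Step 3: how much variance exercise might add.** Assumptions, none from the documents: a proportion p = 0.3 to 0.5 exercises the day before, shifting the marker by s = 0.5 to 1.0 SD.

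- Added variance p(1 - p)s²: 0.3 x 0.7 x 0.25 = 0.05, up to 0.5 x 0.5 x 1 = 0.25 SD².
- Mean shift ps: 0.3 x 0.5 = 0.15, up to 0.5 x 1.0 = 0.5 SD. It is the same in expectation in both randomised arms, so it cancels from GTE vs placebo.
- If s = 0, both are zero.

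**Step 4: effect on power if wk 2 and wk 4 are averaged.** Let f be the proportional increase in wk-2 variance and r the wk 2-wk 4 correlation (assumed 0.3 to 0.7). The SD ratio is sqrt[(2 + f + 2r)/(2 + 2r)], and power is Phi(3.242/ratio - 1.960) starting from 90%.

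| f | SD ratio (r = 0.7 to 0.3) | Power |
|---|---|---|
| 0 | 1.000 | 90.0% |
| 0.05 | 1.007 to 1.010 | about 89.5% |
| 0.10 | 1.015 to 1.019 | 89.2 to 88.9% |
| 0.25 | 1.036 to 1.047 | 87.9 to 87.2% |

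Worked case, f = 0.25 and r = 0.3: ratio = sqrt(2.85/2.60) = 1.047; 3.242/1.047 - 1.960 = 1.136; Phi = 0.872.

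**Step 5: the obese-healthy comparison at wk 2.** If one group exercised at 30% and the other at 50% (the ends of the assumed range), the spurious difference would be (0.5 - 0.3) x s = 0.10 to 0.20 SD for s = 0.5 to 1.0.

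**The case against.** The strongest reply is that the primary contrast, GTE vs placebo in obese adults, is randomised and double-blind with identical wk-2 instructions in both arms. A wk-0 to wk-2 drift is offset by the concurrent placebo arm, and the plan names no uncontrolled pre-post test. This stands. A reader might infer that the gap biases the treatment effect; the documents do not support that.

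A reader might also infer that wk-2 samples will be taken under different physiological conditions. The documents show only different instructions. They do not say how many participants exercise the day before, or that exercise moves endotoxin. This also stands, and it is why every size in the working is conditional.

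The narrower rule may be deliberate: fasting is tied to blood sampling in general, while the exercise rule is tied to two specific procedures. That is possible, and no passages contradict each other. But no rationale is given, and the wk-0 fasting draw and, by inference, the wk-4 draw get the protection anyway.

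Finally, the contrast between 15 and 5 minutes of rest is tempting as a second finding of equal weight. It is not one. The 15 minutes accompany catheter insertion before a 12-hour trial, the 5 minutes precede a single draw, and no wk-4 rest is stated. Nothing in the documents suggests the difference moves any marker.

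**Conclusion.** The gap in the exercise instruction is real but minor. The wk-2 draw lacks an instruction that applies at wk 0 and, by inference from the visit count, at wk 4. If that inference failed, exercise control would be less consistent still and the same clarification would be needed.

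The consequence is a possible loss of precision and a less clean time course and obese-healthy comparison at wk 2. The documents do not allow the size to be estimated. Under the assumed 5-25% added wk-2 variance, with wk 2 and wk 4 averaged and a start at 90%, power falls by about half a point to just under 3 points. The top of that range takes the highest assumed exercise rate and the largest assumed shift together. A contrast based on wk 4 alone would lose nothing. This is an inexpensive improvement and does not threaten the trial's conclusions.

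**What to change.** In Dietary Meeting (section III.D), reword the exercise sentence so that the 24-hour abstention applies before each study visit at which fasting blood is drawn for endotoxin (wk 0, 2 and 4), while still covering the sugar probe tests and the pharmacokinetics trial. State in the Sugar Probe Test section that the wk-4 fasting blood is drawn at that visit, if that is the intention.

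As a secondary harmonisation, specify one common seated rest period before the wk-0, wk-2 and wk-4 fasting draws.

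The cost is one extra instruction to participants and a few minutes at a visit. The change has to be made before the wk-2 samples are collected, because the missing standardisation cannot be restored afterwards.

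### The protocol does not say whether allocated confections may start before the 24-h PK urine is complete; if they may, only the GTE arm can add catechins to the 12-24 h collection

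*Combined protocol and SAP*

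**What the plan says.** All places are in III.D of the combined protocol and SAP unless noted.

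- **Length of the PK trial.** Test Trials: "The second study visit will consist of a 12-h pharmacokinetics trial".
- **Length of its urine collection.** Test Trials: "Urine will be collected between 0-4, 4-8, 8-12, and 12-24 h post-ingestion into provided urinary collection containers". The Pharmacokinetics Trial subsection repeats the same four windows.
- **Start of the intervention.** Test Trials: "Upon completing the pharmacokinetics trial, the intervention phase will begin". No clock time or time of first intake is given.
- **Dispensing.** The Pharmacokinetics Trial subsection, describing what happens after the 12-h trial, says: "Participants will also be provided with a 2-wk supply of GTE-rich or placebo confections". Intervention Phase / Test Confections ties the same step to completion: "Participants will receive a 2-wk supply of confections after completing the pharmacokinetics trial".
- **Regimen.** Pharmacokinetics Trial: "Participants will be advised to consume 6 confections each day (2 per meal; 1 g GTE/d) for the entire 4-week intervention study".
- **Meals for the remaining urine collection.** The same subsection provides "prepared standardized polyphenol-free meals to consume for the remainder of the 24-h urine collection period".

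The PK intake is 3 GTE-rich confections (0.5 g GTE), described without reference to arm. The take-home supply is GTE-rich or placebo, and placebo contains no GTE.

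**The concern.** The last urine window opens when the 12-h trial ends. At that moment participants receive the allocated confections, an instruction to eat them with meals, and meals to eat while urine is still being collected. No passage tells them to hold the confections until the collection ends, and none asks for the time of the first one to be recorded. A participant who follows the text could take allocated confections inside the PK urine window.

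In the GTE arm, that intake would be counted as excretion of the 0.5 g PK intake; in the placebo arm there is nothing to count. A week-0 measure meant to precede treatment would then depend on allocation and on when the participant happened to start. The first objective compares catechin PK in obese and healthy adults, and urinary catechins and metabolites are among its measurements (III.C). Blood sampling stops at 12 h, so the 12-24 h urine is the only later information on elimination.

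**Working it through.** **Plan's own figure.** 6 confections = 1 g GTE, so 3 confections = 3/6 = 0.5 g. This reproduces the stated PK intake.

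**Possible added intake (GTE arm only).** One meal: 2/6 = 0.333 g, and 0.333/0.5 = 67% of the PK intake. Two meals: 0.667 g, or 133%. Placebo: 0 g.

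**Inputs for sizing.** Half-lives of 2.5-5.7 h are from II, Background and Rationale. The following are assumptions: linear first-order elimination, the same urinary fraction for both intakes, a 2-h lag before excretion, and one confection-bearing meal at time *m*.

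With k = ln 2 / half-life, and everything expressed as a share of what the 0.5 g intake would eventually excrete:

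- PK intake excreted in 12-24 h: exp(-10k) - exp(-22k) = 0.060 (2.5 h) or 0.228 (5.7 h)
- PK intake excreted in 0-24 h: 1 - exp(-22k) = 0.998 or 0.931
- Added by a meal at *m* (no later than 22 h): 0.667 × [1 - exp(-(22 - m)k)]; zero if *m* is 22 h or later

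| Meal time | Added (2.5 h; 5.7 h) | Inflation of 24-h recovery | 12-24 h excretion relative to none added |
|---|---|---|---|
| 12 h | 0.625; 0.469 | 0.625/0.998 = 63%; 0.469/0.931 = 50% | 11.4; 3.1 times |
| 20 h | 0.284; 0.144 | 28%; 15% | 5.7; 1.6 times |
| 22 h or later | 0; 0 | 0% | 1.0 |

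**Sensitivity to the lag.** With no lag, one meal at 13 h multiplies 24-h recovery by 1.52-1.64, one at 23 h by 1.08-1.16, and meals at both times by 1.6-1.8.

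**Added variance.** Suppose half of each health group takes one meal at the same time and recovery is inflated by a fraction *f* in those participants. The overlap alone then gives a coefficient of variation of (f/2)/(1 + f/2). For a meal at 12 h (f = 0.50-0.63) this is 20-24%. For a meal at 20 h (f = 0.15-0.28) it is about 7-12%.

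**Possible bias.** Block randomization is not stated to be stratified by health status. If 20 of 40 participants receive GTE and health status is mixed at random over the allocation list, the chance that the obese group has 8 or fewer, or 12 or more, on GTE is 0.34 (hypergeometric). With a 12 to 8 split and every GTE participant eating at 12 h, the health-status difference in mean recovery shifts by (12 - 8)/20 × 0.50 to 0.63 = 0.10 to 0.13 of the uncontaminated value.

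**What stays clean.** Plasma sampling ends at 12 h, and the three urine windows up to 12 h are collected separately. In this model 0-12 h holds (1 - exp(-10k))/(1 - exp(-22k)) = 94% (2.5 h) or 76% (5.7 h) of the PK intake's 24-h excretion.

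**The case against.** The strongest reply is that the protocol never says the intervention starts at 12 h. The sentence on starting follows a paragraph that lists the 12-24 h urine among the PK procedures, and Test Trials also says the PK trial is completed before the intervention. Completing it can naturally include its last urine collection. The polyphenol-free meals, and the warning under Dietary Meeting that polyphenol intake may confound the PK trial, point to a window meant to be free of catechins. A reader might infer that the protocol directs an overlap; the text does not support that. What stands against this reply is that the Pharmacokinetics Trial subsection treats the end of the 12-h trial and the remaining urine collection as separate, dispenses the confections at the former, and controls the meals but not the confections.

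It can also be said that the larger figures depend on the worst meal time. That is right: the range starts at no effect. The lag is an assumption, and the documents give no half-life for the microbial metabolites that they describe as mostly found in urine, so the model does not size that part of the endpoint.

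Third, the PK contrast is obese versus healthy, and the planned ANCOVA for most data includes treatment. If used here, that term would absorb an average difference between arms. It would not remove variation from unrecorded start times.

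Finally, the protocol refers to a study design attachment that is not in the public document and may fix the time of first intake.

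**Conclusion.** The concern holds as an ambiguity in stated timing that permits contamination of one PK urine window in one arm. The possible addition of 0.33 g GTE per meal (67% of the PK intake) follows from the protocol's own regimen. Its effect on 24-h recovery, for one meal, runs from 0% to about 63% depending on meal time and half-life, under linear kinetics, half-lives of 2.5-5.7 h and a 2-h lag. Two meals would add more.

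The main consequence is extra variance in the obese-vs-healthy comparison of urinary elimination. Bias arises only if arm or start time is unbalanced by health status. A reader might take the 50-63% inflation, or the 3- to 11-fold rise in the 12-24 h fraction, as the expected effect. The documents do not support that, because those figures require a meal at 12 h. Nor does this route reach plasma PK, 0-12 h urine or the primary endotoxin outcome. The point is worth correcting before the study starts because the correction is cheap, but it does not threaten the primary analysis.

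**What to change.** The sponsor should reconcile the Test Trials, Pharmacokinetics Trial and Intervention Phase / Test Confections subsections on three points: when the PK trial is complete, when allocated confections begin, and how that relates to the 24-h PK urine. Which schedule to adopt is for the sponsor. The participant instructions should match, and the time of the first allocated confection should be recorded, since overlap cannot be identified without it.

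For the analysis, state in advance that if any overlap occurs, 0-12 h urinary excretion is the main urinary PK comparison for all participants. Report 12-24 h and 0-24 h excretion separately, with overlapping participants identified. Truncating only the affected participants would mix 12-h and 24-h endpoints within one comparison.

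The cost is a wording change and one extra recorded time, with no new visit or sample. If the 0-12 h fallback is used, it gives up 6-24% of modelled 24-h catechin excretion (100% minus 94% or 76%). The loss for microbial metabolites cannot be stated from the documents.
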